11.7 Baseline

All analysis datasets having measurements taken at more than one visit/time point will have baseline flags. Baseline is defined as the latest non-missing measurement prior to IMP administration including repeat assessments and unscheduled visits. In case of multiple results at the same date/time, worst result will be considered as baseline in the following order or hierarchy: Abnormal CS, Abnormal NCS, Normal, Missing.

11.7.1 Change from Baseline

Change between Baseline and post-baseline result will be calculated as:

Change from baseline = Result at Visit X – Baseline Result

11.8 Protocol Deviations

Protocol Deviations will be classified by the Sponsor as 'Important/Major' and 'Not Important'. The deviations will be reviewed during the blinded review meeting and finalized prior to DBL.

11.9 Treatment Compliance

The following variables will be derived for treatment compliance summaries:

- Cumulative IV Planned to be administered (mL) = Planned Dose for Dose 1 (mL) + Planned Dose for Dose 2 (mL) + Planned Dose for Dose 3 (mL)
- Cumulative Actual IV administered (mL) = Total amount infused for Dose 1 (mL) + Total amount infused for Dose 2 (mL) + Total amount infused for Dose 3 (mL)
- Treatment Duration (hours) = End Date and Time of Last Dose – Start Date and Time of First Dose

- Treatment Compliance (%) = $\frac{\text{Cumulative Actual IV Administered}}{\text{Cumulative Planned IV to be Administered}} \times 100.$

Cumulative Planned IV to be Administered

Treatment compliance is based on volume of IV administered, and not IMP dose, hence placebo group will also have this calculation done.

11.10 Medical History and Concurrent Diseases

If a condition has end date prior to first dose of IMP or if end date is missing and the Ongoing status = No, then these will be flagged as Medical / Surgical History. If a condition has end date on or after first dose of IMP or if the Ongoing status = Yes, then these will be flagged as Concurrent Diseases.

11.11 Prior and Concomitant Medications

The following will be the definitions for classification of Prior and Concomitant Medications:

Start Date	End Date	Study Period	Prior / Concomitant
Before IMP	Before IMP	N/A	Prior Medication
Before/After IMP and before Day 14	On or Before Day 14	Treatment Period	Concomitant Medication
Before/After IMP and before Day 14	After Day 14 and On or Before EOS	Treatment Period	Concomitant Medication
After Day 14	After Day 14	Follow-up Period	Concomitant Medication

Note: Worst case scenario of the medication being concomitant to the study drug administration will be considered.

11.12 Adverse Events

A Treatment-Emergent Adverse Event (TEAE) is defined as any AE that begins/ worsens after the first IMP administration.

Related Adverse Events include Possibly, Probably and Definitely Related Adverse Events. Not Related Adverse Events include Probably and Definitely not related Adverse Events.

11.13 Laboratory Assessments

Laboratory results with modifiers will be analyzed with the maximum or minimum value defined without the modifiers. For example, a value of "<5" will be considered as "5" for summaries.

11.14 EKG Measurements

Average of triplicate measurements will be calculated for the following EKG parameters at Screening: Heart rate (bpm), RR (msec), PR (msec), QRS (msec), QT (msec), QTcF (msec).

Average of triplicate measurements = (Measurement 1 + Measurement 2 + Measurement 3) / 3

Note that, if any one measurement is missing, the average of the other 2 measurements will be taken.

11.15 Unit Conversion

For laboratory parameters, units will be converted and summarized in SI units. Reference used for conversion factors will be documented in the respective footnotes.

11.16 Efficacy Endpoints

11.16.1 Hospitalization due to COVID-19

- Days in X = (End Date of X - Start Date of X) + 1
- Cumulative X Days = Sum of all (Days in X)

Note: X denotes Hospitalization, Intensive Care Unit (ICU) and Intubation / Mechanical Ventilations.

- Duration of COVID-19 illness before hospitalization (days) = (Initial Hospitalization Date – COVID-19 confirmation date) + 1

Note: The earliest COVID-19 confirmation date will be considered irrespective of whether or not it is prior to informed consent date.

If a subject has discontinued from the study and X is ongoing or the end date is missing, then X will be considered as ongoing at Day 14 for that subject. For cumulative X days calculation, disposition date will be considered as end date. If a subject had Ongoing Hospitalization at end of study, then end date is considered as subject's disposition date.

Note: X denotes Hospitalization, Intensive Care Unit (ICU) and Intubation / Mechanical Ventilations.

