11.3.4 Repeat Assessments

If there are any repeat assessments, they will be logged as unscheduled visits and the reason for unscheduled visit will be marked as repeat assessment. In such cases, these unscheduled visits will be mapped to the visit for which repeat assessment was taken. In case of multiple repeat assessments on the same day, the latest assessment will be considered for analysis.

For WHO Severity scores, if there are more than one repeat assessments on the same day, then highest non-missing score will be considered for analysis.

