11.5 Discontinued Subjects

Discontinued subjects will have safety assessments taken at Early Withdrawal visits. These will be presented separately and will not be combined with EOS if results are available.

The reason for discontinuation from the study will be mapped in the analysis as follows:

Primary reason for early discontinuation (As in CRF)	Reason for early termination from the study
Subject withdrew consent	Subject withdrew consent
Unacceptable AE	Unacceptable AE
Pregnancy	Pregnancy
Subject is unwilling or unable to continue the study or is lost to follow up	Subject unwilling / lost to follow-up
Subject is non-compliant with study procedures/study protocol	Protocol Deviation
Investigator decides that withdrawal from the study is in the best interest of the subject	At the discretion of the Investigator
Any clinically significant change in subject's medical condition (at the discretion of the Investigator)	At the discretion of the Investigator due to change in medical condition
Treatment unblinded	Treatment Unblinded
Sponsor decision to end the study	Sponsor decision to end the study
Death	Death
Other	Other

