11.16.4 WHO Severity Scores

The 9-point WHO classification scheme from 0 to 8 for COVID-19 pneumonia will be applied to grade the severity of illness as follows:

- *8 - Death*
- *7 - Mechanical ventilation or extracorporeal membrane oxygenation (ECMO), vasopressor support, dialysis/renal replacement therapy (RRT)*
- *6 - Intubation with mechanical ventilation, a mask with a reservoir or oxygen with high-flow nasal goggles.*
- *5 - Noninvasive ventilation (continuous positive airway pressure [CPAP] or bilevel positive airway pressure [BiPAP]) or high-flow oxygen*
- *4 - Oxygen by mask or nasal*
- *3 - Hospitalized with no oxygen therapy*
- *2 - Limitation of activity*
- *1 - Infected without limitations*
- *0 - No clinical or virologic evidence of COVID-19 infection*

Higher WHO Severity Score indicates worse conditions.

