12.9.2.6 Comparison of Days in Hospital, ICU and Ventilation

Cumulative number of days for Hospitalization, ICU and Intubation / Mechanical Ventilation will be compared across treatment groups using non-parametric Wilcoxon Rank Sum test. The test will be two-sided with level of significance of 5%. Descriptive summaries of cumulative number of days,

difference in treatment groups, 95% CI and unadjusted p-value will be reported. P-value will be from testing the null hypothesis that mean of cumulative days across treatment groups are same.

Reference SAS Program:

```
proc npar1way data=<data>;
  class <treatment>;
  var <days>;
run;
```

In DDP: Table 14.2.6.3 and Table 14.2.6.4

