12.10.2 Summary of Death

Number and percentage of deaths due to any cause, AE leading to Death by preferred term, Death due to COVID-19 (WHO score = 8) by visit will be summarized by treatment groups. Percentages are based on Safety analysis set.

In DDP: Table 14.3.2.3

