16.1 Summary of Statistical Analyses

Endpoints	Analysis Set	Primary Analyses	Supportive Analyses
Incidence of SAEs in rhu-pGSN vs placebo groups	Safety analysis set	Descriptive Summaries	-
Proportion of subjects alive not on vasopressors, mechanical ventilator, and dialysis on Day 14.	FAS (primary), Per-Protocol analysis set	Cochran-Mantel-Haenszel (CMH) method	-
Adverse Events, Clinically Significant Laboratory Results	Safety analysis set	Descriptive Summaries	-
Change in WHO Severity Score	FAS, Per-Protocol analysis set	Shift summaries, Box Plots, MMRM	-
Mortality Rate and Time to Death	FAS (primary), Per-Protocol analysis set	Log Rank Test, Cox Regression Model, Kaplan-Meier Curve	-
Proportion of Subjects alive without support	FAS (primary), Per-Protocol analysis set	CMH	-
Days on the Ventilator	FAS (primary), Per-Protocol analysis set	Descriptive Summaries, Wilcoxon Rank Sum Test	-
Hospitalization and ICU days	FAS (primary), Per-Protocol analysis set	Descriptive Summaries	-
Plasma Concentration	PK analysis set	Descriptive Summaries and Plots	
PK Parameters	PK analysis set	Descriptive Summaries	-
Immunogenicity	PK analysis set	Descriptive Summaries	-
Biomarkers	Safety analysis set	Descriptive Summaries	-

17 Change Log

Version	Authored by	Change Date	Change Details	Reviewed by	Review Date
1.00	[name] [name]	05-Aug-2021	First version approved	[name]	05-Aug-2021

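### Secondary and sensitivity analyses only: the SAP has no death-specific rule, so its general discontinuation rules shorten day counts at death, leave WHO scores after death missing, and leave early deaths unclear in the per-protocol set

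*SAP*

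**What the plan says.** **Day counts.** SAP 11.16.1 computes hospital, ICU and ventilator time as "Days in X = (End Date of X - Start Date of X) + 1", summed over episodes. If a subject has left the study with an episode open or undated, "For cumulative X days calculation, disposition date will be considered as end date". Such an episode is also labelled ongoing at Day 14, but that label does not enter the count. SAP 11.5 states "The reason for discontinuation from the study will be mapped in the analysis as follows", and its table includes death. SAP 12.9.2.6 then says "Cumulative number of days for Hospitalization, ICU and Intubation / Mechanical Ventilation will be compared across treatment groups using non-parametric Wilcoxon Rank Sum test", two-sided at 5%, with no term for death. SAP 16.1 lists "Hospitalization and ICU days" with descriptive summaries only and names the Wilcoxon test for ventilator days alone.

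**WHO score.** SAP 11.16.4 makes death the top value, 8, and adds "Higher WHO Severity Score indicates worse conditions". An 8 can be recorded: SAP 12.10.2 says "Death due to COVID-19 (WHO score = 8) by visit will be summarized by treatment groups", and for same-day repeats SAP 11.3.4 says "if there are more than one repeat assessments on the same day, then highest non-missing score will be considered for analysis". No rule carries the 8 to later visits. For the shift tables, SAP 11.3.3 puts scheduled visits after discontinuation into a missing category. SAP 12.9.2.1.3 fits a mixed model (MMRM) to scores collected at scheduled visits, assuming missing at random.

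**Per-protocol set.** SAP 10.6 requires that the subject completed Day 14, took three doses and had no important deviation. Protocol 11.1 requires three doses and evaluability for the Day 14 endpoint. Neither says where a death after dose 3 and before Day 14 belongs.

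**Where death is handled properly.** It is a failure in the primary FAS analysis (SAP 12.9.1.1) and in the FAS alive-without-support analyses (12.9.2.3), and it is the event in time to death (11.18, 12.9.2.2).

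**The concern.** In a trial of severe COVID-19 pneumonia, death cuts short both the stay and the series of scores. A patient who enters hospital on Day 1 and dies on Day 5 has 5 - 1 + 1 = 5 hospital days. One discharged alive on Day 14 has 14. The Wilcoxon test ranks the death as the better result. In the WHO analyses, the worst state on the scale is replaced by a missing cell in the shift tables, or by a value that the model implies from patients still alive.

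If deaths differ between arms, these results can understate a survival benefit or understate harm. If early deaths were also left out of the per-protocol set, the robustness check of the primary result would lose part of the outcome it is meant to check.

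**Working it through.** The plan gives no figure for these analyses. Its sample-size figure does reproduce. With 27 per arm, 20% vs 5% and one-sided alpha 0.2, the pooled standard error is sqrt(2 × 0.125 × 0.875 ÷ 27) = 0.0900 and the unpooled one is sqrt((0.16 plus 0.0475) ÷ 27) = 0.0877. Power is Φ((0.15 minus 0.8416 × 0.0900) ÷ 0.0877) = 80.1%. Nothing below changes it.

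**Assumed inputs.** The documents give no mortality, death timing or length of stay. Survivor stay and day of death are taken as lognormal with log SD 0.5; the survivor median is 14 days. Deaths of 20% vs 5% treat the SAP 4.2 proportions as failures that are all deaths; 10% vs 2.5% is half of that. SAP 4.2 does not call these proportions failures. It speaks of surviving subjects, but the direction fits only failures.

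**(a) Hospital days, equal survivor stays.** Let q be the death proportion and θ the chance that a fatal stay is shorter than a survivor's. The chance that a rhu-pGSN patient ranks better (ties count half) is

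P = 0.5 + (q_drug - q_placebo)(θ - 0.5).

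With median death Day 7, θ = Φ(ln 2 ÷ (0.5√2)) = 0.8365. With Day 21, θ = Φ(ln(14 ÷ 21) ÷ (0.5√2)) = 0.283. With Day 14, θ = 0.5. If all deaths fall within the horizon and take the worst rank, θ = 0.

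| Deaths, placebo vs drug | Death Day 7 | Day 14 | Day 21 | Worst rank |
|---|---|---|---|---|
| 10% vs 2.5% | 0.475 | 0.50 | 0.516 | 0.54 |
| 20% vs 5% | 0.450 | 0.50 | 0.532 | 0.575 |

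For the first cell: 0.5 minus 0.075 × 0.3365 = 0.475. Simulating 200,000 patients per arm gives the same values to within about 0.002.

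With median death Day 7 and shorter stays on the drug, simulation gives, raw vs Day 28 worst rank:
- 10% vs 2.5% deaths: 0.53 vs 0.59 (stays 10% shorter), 0.66 vs 0.71 (30% shorter).
- 20% vs 5% deaths: 0.50 vs 0.62, and 0.63 vs 0.72.

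In trials of 30:30 with 10% vs 2.5% deaths and equal stays, the raw test is significant for placebo in about 5%, against a nominal 2.5%. It is significant for the drug in about 7% raw vs 22% worst rank if stays are 10% shorter, and 57% vs 81% if 30% shorter.

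Ventilator days have no fixed direction: raw P runs from 0.49 to 0.53 at 10% vs 2.5% deaths and from 0.47 to 0.57 at 20% vs 5%. It depends on how many survivors are ventilated and whether a prevented death means no ventilation or a longer course. The same reasoning applies to ICU days.

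**(b) WHO score.** If survivors have the same mean score s in both arms, carrying 8 gives a difference of (q_drug - q_placebo)(8 - s). For 20% vs 5% and s = 2 to 4 this is -0.15 × 6 = -0.9 to -0.15 × 4 = -0.6. Using survivors only, it is 0. An unstructured repeated-measures model on simulated 30:30 trials gave these Day 14 differences:
- Deaths 3/30 vs 1/30: -0.02 to -0.22 under missing at random, -0.34 to -0.38 with 8 carried.
- Deaths 6/30 vs 2/30: -0.16 to -0.40, against -0.63 to -0.82.

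The model implied a mean score of 2.9 to 5.0 for patients already dead. There were 40 trials in each of 12 cases; the direction was the same in all, but the sizes depend on the assumed trajectories.

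**(c) Per-protocol set.** If failures f include early deaths d and these are excluded, the failure proportion becomes (f - d)/(1 - d). With f = 0.20 and 0.05:
- d = 25% of f: 0.15 ÷ 0.95 = 15.8% vs 0.0375 ÷ 0.9875 = 3.8%, 12.0 points.
- d = 50% of f: 0.10 ÷ 0.90 = 11.1% vs 0.025 ÷ 0.975 = 2.6%, 8.5 points.
- d = 75% of f: 0.05 ÷ 0.85 = 5.9% vs 0.0125 ÷ 0.9625 = 1.3%, 4.6 points.

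The full contrast is 15 points. Deaths before dose 3 are excluded under both definitions, so these figures are the most that the ambiguity could cost.

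**The case against.** **Rules do exist.** A reader might infer that the SAP says nothing about subjects who die. That is too strong: the disposition-date rule and the missing category in 11.3.3 both apply to them. What is absent is any rule that treats death as a bad outcome.

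**Direction and timing.** The pull in hospital stay needs early deaths, and follow-up runs to Day 90. This objection stands.

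**A different endpoint.** The protocol endpoints are durations. Worst rank makes each a composite of death and duration, so much of the rise from 57% to 81% is an assumed mortality benefit entering the test, not bias removed. Mortality is already reported through time to death, alive-without-support and the death summaries. This stands too, and it is why worst rank belongs beside the raw days and not in their place. It does not rescue the raw test, which still ranks an early death as a good result.

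**Scope of the WHO analysis.** SAP 13 limits the change analysis to scheduled visits through Day 14. However, the shift tables and box plots in 12.9.2.1 run to Day 90, so later visits also need a rule.

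**Per-protocol membership.** SAP 11.17 flags per-protocol subjects whatever their disposition, 12.9.1.1 repeats its failure rule in that set, and membership is settled at blinded review. These points favour keeping early deaths, but none defines completion of Day 14.

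**Weight.** SAP 8.2 already urges caution with secondary tests, and the survival tables limit misreading. Both are fair.

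**Conclusion.** The point holds for secondary and sensitivity analyses only. Followed as written, the rules rank an early in-hospital death above a later live discharge and treat the WHO scores of dead patients as missing. Under the assumptions above, the hospital-stay statistic lies about 0.05 to 0.12 below its worst-rank counterpart when the median death is on Day 7. The Day 14 WHO difference is smaller in size under the missing-at-random model than with 8 carried.

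Three stronger readings are not supported.
- That the primary result is biased: SAP 12.9.1.1 counts death as failure in the FAS.
- That the stay comparison will reverse: with stays 10% shorter on the drug, raw P fell below 0.5 only at 20% vs 5% deaths with median death Day 5 (0.485), and late deaths push the other way.
- That the per-protocol set excludes early deaths: the two definitions are ambiguous and need reconciling, and even full exclusion leaves 4.6 to 12.0 points in favour of the drug in the cases worked.

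The mismatch between SAP 12.9.2.6 and 16.1 rests on the text alone. Every magnitude rests on assumed death rates, death timing, stays and score trajectories, and on reading 20% vs 5% as failure proportions.

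**What to change.** **(a)** Keep the raw-day results, with deaths by arm shown beside them. Add a Wilcoxon analysis with a fixed horizon, for example Day 28: death by the horizon takes the worst rank with all such deaths tied, longer stays are capped, and never-ventilated or never-ICU patients count as 0 days. State that it is a composite of death and duration. Reconcile SAP 12.9.2.6, which tests all three durations, with 16.1, which names the test for ventilator days only.

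**(b)** Assign WHO score 8 at every scheduled visit after death in the shift tables and the MMRM. Report the MMRM without carry-forward as a sensitivity analysis.

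**(c)** Reconcile SAP 10.6 with protocol 11.1 so that a subject with three doses, no important deviation and death before Day 14 stays in the per-protocol set as a failure.

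**Cost.** SAP wording and derivations from dates already collected; the protocol endpoints do not change. The added Wilcoxon result is not in days. If deaths are equal between arms, it slightly dilutes a true difference in stay (0.67 raw vs 0.66 at 10% deaths per arm and stays 30% shorter). Carrying 8 makes the scores more skewed. SAP 13 refers to database lock in the past tense, so any of these changes made after unblinding must be labelled post hoc.

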### 5.2.2. Secondary Endpoints

- Safety and tolerability
  - Incidence, causality, and severity of AEs (graded according to the National Cancer Institute [NCI] Common Terminology Criteria for Adverse Events [CTCAE] version 5.0) in rhu-pGSN vs placebo groups
  - Frequencies of new or worsening clinically significant laboratory abnormalities in rhu-pGSN vs placebo groups
  - Mortality rate irrespective of cause at Days 28 and 90
- Efficacy
  - Daily change in 9-point WHO severity score through at least Day 14 (including after discharge, where feasible)
  - All-cause mortality at Days 28 and 90; time to death (Kaplan-Meier survival analysis)
  - Proportion of subjects alive on Days 7, 14, 28, 60, and 90 without:
    - Ongoing use of vasopressors
    - Ongoing intubation/mechanical ventilation
    - Ongoing residence in an ICU
    - New ongoing need for dialysis/renal replacement therapy (RRT)
  - Proportion of subjects discharged to home or immediate prior residence by Day 28
  - Days on the ventilator
  - Length of stay (LOS) in hospital and in ICU (days)
  - Re-admission to an acute-care hospital up to Day 90
- PK
  - PK for rhu-pGSN including maximum concentration ( $C_{max}$ ), time to maximum concentration ( $T_{max}$ ), terminal half-life ( $T_{1/2}$ ), area under the curve from time zero to 8 hours ( $AUC_{0-8}$ ), area under the curve from time 0 to infinity ( $AUC_{inf}$ ) for Dose #1 within 15 minutes predose, and at 1 ( $\pm 15$  min), 2 ( $\pm 15$  min), 6 ( $\pm 30$  min), and 12 ( $\pm 30$  min) hours after end of administration (but prior to Dose #2); for Dose #3 within 15 minutes predose, and at 1 ( $\pm 15$  min), 2 ( $\pm 15$  min), 6 ( $\pm 30$  min), 12 ( $\pm 30$  min) and 24 ( $\pm 30$  min) hours after the end of administration (participants refusing these blood samplings can enter and remain in the trial).
- Immunogenicity
  - Presence of anti-pGSN antibodies on Days 1 (predose), 28, and 90

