## 6. INVESTIGATIONAL PLAN

### 6.1. Overall Study Design

This is a 2-part, randomized, double-blind, placebo-controlled, multicenter Phase 2 study to evaluate the efficacy and safety of rhu-pGSN plus SOC in subjects with severe COVID-19 pneumonia. Potential subjects hospitalized with pneumonia and laboratory-confirmed (reverse transcription polymerase chain reaction [RT-PCR+]) or highly suspected (compatible with at least bilobar lung involvement without any other plausible diagnosis) COVID-19 etiology will be screened for Part 1 within 24 hours of reaching a WHO severity score of 4 to 6, whether the severity score is attained on admission or during hospitalization, or for Part 2, within 24 hours of intubation without ECMO with a WHO severity score of 6 or 7.

The 9-point WHO classification scheme for severe COVID-19 pneumonia will be applied to grade the severity of illness as follows:

- 8 Death
- 7 Mechanical ventilation or ECMO with either vasopressor support or dialysis/RRT
- 6 Intubation with mechanical ventilation, a mask with a reservoir or oxygen with high-flow nasal goggles but without vasopressor support or dialysis/RRT
- 5 Noninvasive ventilation (continuous positive airway pressure [CPAP] or bilevel positive airway pressure [BiPAP]) or high-flow oxygen
- 4 Oxygen by mask or nasal
- 3 Hospitalized with no oxygen therapy
- 2 Limitation of activity
- 1 Infected without limitations
- 0 No clinical or virologic evidence of COVID-19 infection

Once informed consent is obtained, the following assessments/procedures will be performed:

1. Record medical history, including concomitant medications and current clinical status
2. Perform pregnancy test (urine or blood) for women of childbearing potential
3. Collect pretreatment blood samples for measurement of baseline pGSN and for analysis of antibodies against pGSN
4. Calculate the CURB-65 score (Confusion, Urea >7 mmol/L, Respiratory rate ≥ 30/min, Blood pressure systolic <90 or diastolic <60, and age ≥ 65 years) at presentation ([Appendix A](#))
5. A RT-PCR test to confirm the diagnosis of COVID-19 should be documented during the current illness leading to the present hospitalization; if RT-PCR test is not done prior to screening, the test is to be performed during screening before randomization (result might

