4.5 Inclusion/Exclusion Criteria

4.5.1 Inclusion Criteria

To be considered eligible to participate in this study, a subject must meet all the inclusion criteria listed below:

- 1) Hospitalized with laboratory-confirmed (RT-PCR+) or highly suspected (compatible with at least bilobar lung involvement without another plausible diagnosis) COVID-19
- 2) Age ≥ 18 years
- 3) Weight ≤ 100 kg
- 4) Within 24 hours of reaching a WHO severity score of 4-6 either:
 - a) At admission
 - b) While already hospitalized.
- 5) Informed consent obtained from subject/next of kin/legal proxy
- 6) Primary admitting diagnosis of pneumonia supported by a compatible clinical presentation with a documented infiltrate consistent with pneumonia on CXR or CT, as assessed by the admitting emergency department (ED), clinic, or ward physician or equivalent caregiver
 - a) Recommended (not mandatory) guidance/discretionary criteria defining patients with pneumonia satisfying all 4 categories below:
 - i) At least 2 symptoms: difficulty breathing, cough, production of purulent sputum, or chest pain
 - ii) At least 2 vital sign abnormalities: fever, tachycardia, or tachypnea (thresholds -- fever: oral or core temperature $>100.4^{\circ}\text{F}$ [38°C]; heart rate >100 beats/min; respiratory rate >24 /min)
 - iii) At least one finding of other clinical signs and laboratory abnormalities: hypoxemia (O_2 saturation $<90\%$), clinical evidence of pulmonary consolidation, or leukocytosis $\geq 1.5 \times 10^4$ or leukopenia $<4 \times 10^3$
 - iv) Chest imaging or CT chest showing at least bilobar pulmonary infiltrates

- (1) Principal Investigator (PI) to note radiologic findings in the eCRF
- (2) Radiology report to be placed in the eCRF
- (3) A copy of the radiograph attached to be saved for review

b) A hyperinflammatory status (defined by increased ferritin $\geq 500 \mu\text{g/L}$, D-dimer $\geq 1000 \text{ ng/mL}$, or CRP $\geq 75 \text{ mg/L}$)

7) During the course of the study starting at screening and for at least 6 months after their final study treatment:

- a) Female subjects of childbearing potential must agree to use 2 medically accepted birth control methods
- b) Male subjects with a partner who might become pregnant must agree to use reliable forms of contraception (i.e., vasectomy, abstinence), or an acceptable method of birth control must be used by the partner
- c) All subjects must agree not to donate sperm or eggs (ovocytes)

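### Hospital, ICU and ventilator days are counted from episode start, so the between-arm comparison includes days before first dose; this costs precision, mainly for hospital days

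*SAP*

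**What the plan says.** Protocol 5.2.2 lists "Length of stay (LOS) in hospital and in ICU (days" and days on the ventilator as secondary efficacy endpoints, without naming a starting point.

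SAP 11.16.1 supplies one. Each episode is "Days in X = (End Date of X - Start Date of X) + 1", the total is "Cumulative X Days = Sum of all (Days in X", and "X denotes Hospitalization, Intensive Care Unit (ICU) and Intubation / Mechanical Ventilations". First IMP date does not appear in these formulas. For hospitalization the start is admission: the neighbouring derivation of illness before hospitalization works from the same date, "Initial Hospitalization Date – COVID-19 confirmation date) + 1".

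SAP 12.9.2.6 then states: "Cumulative number of days for Hospitalization, ICU and Intubation / Mechanical Ventilation will be compared across treatment groups using non-parametric Wilcoxon Rank Sum test". It specifies a two-sided 5% test and reports a treatment difference with a 95% CI. The summary table in SAP 16.1 differs: it names the Wilcoxon test for ventilator days only and lists hospital and ICU days as descriptive.

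Entry is tied to the WHO score, not to admission. Protocol 6.1 screens within 24 hours of the qualifying score, "whether the severity score is attained on admission or during hospitalization", and SAP 4.5.1 admits a subject who qualifies "While already hospitalized". No criterion limits earlier days in hospital.

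Elsewhere the clock starts at first dose. Protocol 6.1 makes that day the analysis baseline, and SAP 11.4 (study duration), 11.6.1 (start day) and 11.18 (time to death) all use first IMP date.

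**The concern.** A treatment comparison should rest on time that treatment can influence. As derived, the totals add the post-dose course to a pre-dose stretch that varies between subjects for unrelated reasons. Two subjects with the same course after dosing can have very different totals.

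Nothing planned would show how far the arms differ on that stretch. The Wilcoxon test takes no covariate. The demographic and baseline tables (SAP 12.4 and 12.5) contain no row for time from admission to first dose. The one related summary, duration of illness before hospitalization (SAP 12.9.2.5), ends at admission. Hospital dates are listed by subject, so a reader could reconstruct the imbalance, but no table presents it. At stake are the precision and readability of secondary endpoints. The primary Day 14 endpoint does not use these counts.

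**Working it through.** The documents give no variance, power or expected stay for these endpoints, so there is no figure to reproduce. The check has five steps.

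**1. What the formula does (illustrative dates).** Admission 1 January, first dose 7 January, discharge 16 January.
- SAP formula: 16 − 1 + 1 = 16 days.
- Counted from first dose: 16 − 7 + 1 = 10 days.
- Six of the 16 days precede treatment. A subject admitted on 7 January with the same later course scores 10 under either rule.

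**2. How much pre-dose time the entry windows allow (Protocol 6.1 and 6.5).** In Part 1, 24 h from the qualifying score to screening, with consent inside that window, plus 12 h from consent to randomization, plus 12 h from randomization to dosing: 24 + 12 + 12 = 48 h. On the natural reading, a Part 1 subject was at score 3 or lower before reaching 4-6, hence without oxygen and not ventilated. Pre-dose ventilator time is then about 2 days at most. The same usually holds for ICU days, unless the subject was in the ICU at score 3 or the window is read more loosely. Pre-dose hospital days have no such bound. This SAP does not cover Part 2, where the corresponding limit is 24 + 12 = 36 h from intubation.

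**3. Effect on variance.** If pre-dose and post-dose days are independent, variance ratio = 1 + SDpre²/SDpost², and effective sample size is its inverse. All SDs are assumptions, except that a quantity confined to 0-2 days cannot have an SD above 1.

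| Measure | SDpre | SDpost | Variance ratio | Effective sample size |
|---|---|---|---|---|
| Hospital, low | 2 | 10 | 1 + 4/100 = 1.04 | 96% |
| Hospital, middle | 3 | 7 | 1 + 9/49 = 1.18 | 84% |
| Hospital, high | 5 | 7 | 1 + 25/49 = 1.51 | 66% |
| Ventilator (usually ICU) | 1 | 10 | 1 + 1/100 = 1.01 | 99% |
| Ventilator (usually ICU) | 1 | 7 | 1 + 1/49 = 1.02 | 98% |

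**4. Chance imbalance.** With 30 per arm, the standard error of the arm difference in mean pre-dose days is SDpre × √(2/30): 0.52, 0.77 and 1.29 days for SDpre of 2, 3 and 5.

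**5. The planned test.** The ratio in step 3 concerns means, whereas the SAP plans a rank test. The Wilcoxon test was therefore simulated: 30 per arm, two-sided 5%, 4,000 runs per scenario, assumed post-dose medians of 10 and 7 days, lognormal with log-scale SD 0.6.

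| Pre-dose days added (assumed) | Power | Type I error |
|---|---|---|
| None | about 59% | near 5% |
| 0-2 | about 57% | 0.054 |
| Mean 3 | about 44% | 0.050 |
| Mean 6 | about 33% | 0.045 |

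The last two rows use a geometric distribution, whose SD is √(1−p)/p: √0.75 × 4 = 3.5 days for mean 3 and √(6/7) × 7 = 6.5 days for mean 6. The mean-6 row therefore lies beyond the SD range in step 3.

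**The case against.** The strongest reply is that the protocol endpoint is length of stay, that counting from admission is the conventional meaning, and that the SAP implements it literally. That stands: the SAP does not depart from its protocol here. The point is that a conventional description of stay is a less precise measure of treatment effect than post-dose days.

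Second, admission must be for pneumonia with a documented infiltrate (Protocol 7.2), so long unrelated stays before in-hospital COVID-19 are largely excluded. That also stands. It makes a pre-dose SD of 5 days look high, and the documents cannot settle it.

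Third, the decision weight is low. These are secondary endpoints without multiplicity control, to be read with caution under SAP 8.2, and SAP 16.1 plans only descriptive summaries for hospital and ICU days. This limits the consequence, but SAP 12.9.2.6 does test all three, so the two sections need reconciling.

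A reader might infer that pre-dose days bias the comparison, dilute the expected mean difference or raise the false-positive rate. The documents do not support that. Nearly all of these days precede 1:1 randomization, and the remainder, at most 12 h between randomization and dosing, falls under blinding. An arm difference in them is ordinary sampling error, which the test already allows for; simulated type I error was 0.045-0.054.

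**Conclusion.** The point holds as a loss of precision, mainly for hospital days. SAP 11.16.1 has no cut at first dose, prior hospital stay has no stated limit, and first dose is the time origin used elsewhere. Under the assumed SDs (2-5 days before dosing, 7-10 after, independent), the variance of hospital days rises 4% to 51%. The Wilcoxon simulation agrees in direction, with a loss ranging from negligible to substantial depending on a distribution that the documents do not give.

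Two stronger readings should be resisted. One is that all three comparisons suffer alike: for ventilator days, and usually ICU days, the entry window limits pre-dose time to about 2 days and the variance increase to about 1-2%, which is negligible. The other is that the trial loses a third of its effective sample size: the 66% figure is the extreme of an assumed range, from a means-based approximation, for hospital days only. Type I error, the expected difference in mean days and the primary endpoint are unaffected.

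**What to change.** In SAP 11.16.1 and 12.9.2.6, for the between-arm comparison:

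- Count calendar days in X from the later of the start date of X and first IMP date. Episodes that ended before first dose contribute zero.
- Count each calendar day once. The +1 per episode now counts a shared date twice when one episode ends and the next starts on the same day. This is a minor matter, settled by the same rule.
- Add days from admission to first dose, by arm, as a row in the baseline table.
- Keep total stay from admission as a descriptive listing.
- Make SAP 16.1 agree with 12.9.2.6 on which day counts are tested.

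The cost is SAP wording and a small change to one derivation. Episode dates and first IMP date are already used in SAP 11.6.1 and 11.16.1. The blinded review meeting in SAP 9.4 already covers changes to planned analyses, so the change can be recorded before unblinding. The one downside is that the compared stays will be shorter than conventional length of stay, so the tables should label them as days from first dose.
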